8.2. Setting

The study will enroll patients according to the eligibility criteria in participating countries across Europe. The recruiting centers will be representative of each country involved in terms of care management systems, of size and of practices (at least when performing feasibility).

Any patient who meets the eligibility criteria will be invited to participate in the study with no selection by the investigators. The enrollment visit will be performed at the time of the patients' inclusion, after the patients' acceptation of enrollment in the study.

Data will come from medical records and will be collected in routine clinical practice. The enrollment visit will comprise a first section on patients' eligibility for every patient whatever pool they belong to and a second section depending on the treatment started (SU or AXI) at the inclusion.

For patients enrolled in the study when AXI is started as a 2^{nd} line therapy, a retrospective section will be completed at patients' inclusion, to collect data on SU 1^{st} line treatment.

For patients who start AXI when SU is discontinued during the study, the AXI initiation visit will resume baseline data that need to be updated.

Follow-up will be ensured during visits in the context of usual patients' care management (non-interventional study). No visits will be required by the protocol of the study. As long as the

patients are treated with SU or AXI, every visit to the center will be recorded. In accordance with ESMO guidelines and physicians clinical practice is real life, follow-up visits are approximately expected:

- during SU treatment: every 6 weeks (every cycle) with tumor assessment approximately every 3 months with respect to the clinical practice
- during AXI treatment: every 4 weeks (every cycle) with tumor approximately assessment every 2 months with respect to the clinical practice

[figure not shown]
When patients come off SU treatment (i.e. are not receiving AXI) or come off Axitinib (after receiving the SU-AXI sequence) they will be followed up every 6 months (separate form) for survival until the end of the study.

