Scenarios involving exposure to a drug under study, including exposure during pregnancy, exposure during breast feeding, medication error, overdose, misuse, extravasation; lack of efficacy; and occupational exposure	All (regardless of whether associated with an AE), except occupational exposure	All (regardless of whether associated with an AE)

For each AE, the investigator must pursue and obtain information adequate both to determine the outcome of the adverse event and to assess whether it meets the criteria for classification as a SAE (see section "Serious Adverse Events" below)

Safety events listed in the table above must be reported to Pfizer within 24 hours of awareness of the event by the investigator regardless of whether the event is determined by the investigator to be related to a drug under study. In particular, if the SAE is fatal or life-threatening, notification to Pfizer must be made immediately, irrespective of the extent of available event information. This timeframe also applies to additional new (follow-up) information on previously forwarded safety event reports. In the rare situation that the investigator does not become immediately aware of the occurrence of a safety event, the investigator must report the event within 24 hours after learning of it and document the time of his/her first awareness of the events.

For safety events that are considered serious or that are identified in the far right column of the table above that are reportable to Pfizer within 24 hours of awareness, the investigator is obligated to pursue and to provide any additional information to Pfizer in accordance with this 24-hour timeframe. In addition, an investigator may be requested by Pfizer to obtain specific

follow-up information in an expedited fashion. This information is more detailed than that recorded on the eCRF of the study. In general, this will include a description of the adverse event in sufficient detail to allow for a complete medical assessment of the case and independent determination of possible causality. Any information relevant to the event, such as concomitant medications and illnesses must be provided. In the case of a patient death, a summary of available autopsy findings must be submitted as soon as possible to Pfizer or its designated representative.

Reporting period

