For each patient, the safety event reporting period begins at the time of the patient's first dose of Sunitinib and/or Axitinib or the time of the patient's informed consent if s/he is already exposed to Sunitinib and/or Axitinib, and lasts through the end of the observation period of the study, which must include at least 28 calendar days following the last administration of a drug under study, a report must be submitted to Pfizer Safety (or its designated representative) for any of the types of safety events listed in the table above occurring during this period. If the investigator becomes aware of a SAE occurring at any time after completion of the study and s/he considers the SAE to be related to Sunitinib and/or Axitinib, the SAE also must be reported to Pfizer Safety.

Causality assessment

The investigator is required to assess and record the causal relationship. For all AEs, sufficient information should be obtained by the investigator to determine the causality of each adverse event. For AEs with a causal relationship to *Sunitinib and/or Axitinib*, follow-up by the investigator is required until the event and/or its sequelae resolve or stabilize at a level acceptable to the investigator, and Pfizer concurs with that assessment.

An investigator's causality assessment is the determination of whether there exists a reasonable possibility that *Sunitinib and/or Axitinib* caused or contributed to an adverse event. If the investigator's final determination of causality is "unknown" and s/he cannot determine whether *Sunitinib and/or Axitinib* caused the event, the safety event must be reported within 24 hours.

If the investigator cannot determine the etiology of the event but s/he determines that Sunitinib and/or Axitinib did not cause the event, this should be clearly documented on the eCRF of the study and the NIS AEM Report Form.

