1.2. Study plan

Variable	At SU initiatio n visit	At SU follow-up visit	At AXI initiation visit	At AXI follow- up visit	Long term follow up
Patient demographics	x		x*		
Performance status	х	х	х	х	X
MSKCC risk, Heng risk	x		x		
Description of primary tumor	x		x*		
Metastasis	x		x		
Comorbidities	x		x		
Lab tests	x	x	x	х	
Blood Pressure measurement / antihypertensive treatment	х	х	х	x	
Electrocardiogram	x		х		
Echocardiography	x		x		
Sunitinib therapy	x	x	X**		
Axitinib therapy			x	x	
Other anti tumor treatment	x	x	x	x	X
Concomitant treatment	x	x	x	x	
Tumor Response		x		х	x
Safety	x	x	x	х	
Quality of life (FKSI-19, and MH and RE domains of SF-36)			х	х	
Death		х		X	x

^{*:} only if patient is enrolled at Axitinib start / **: retrospective records

ADONIS CRF

Subject ID:

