4. AXITINIB SECOND LINE VISITS

4.1. AXITINIB INITIATION VISIT

Axitinib Initiation Date / / 20 (DD/MM/YYYY)	Patient identifier 🖳				
This visit is performed when the patient starts Axitinib in second line.					
- If the patient was enrolled in the study when Sunitinib started in first lin need an update	- If the patient was enrolled in the study when Sunitinib started in first line, please only fill in sections that need an update				
- If the patient is enrolled at this stage (Axitinib start) please complete ever retrospective section that you will find at the end of the visit	ry section as well as the Sunitinib				
Patient characteristics at Axitinib initiation					
Weight Kg (only for patient enrolled at Sunitinib start),					
ECOG					
Eastern Cooperative Oncology Group (ECOG) available	□ Yes □ No				
If yes,					
□0 □1 □2 □3 □4					
Karnofsky performance status					
Karnofsky status available	☐ Yes ☐ No				
Classification to determine a patient's performance status					
Normal status, no complaints, no evidence of disease	□ 100%				
Minor signs and symptoms of disease	90%				
Normal activities with efforts	□ 80%				
Unable to carry on normal activity, unable to work, able to care for self	□ 70%				
Requires occasional assistance	□ 60%				
Requires nursing and medical care and assistance, not permanently bedridden	□ 50%				
Bedridden, requires special care	☐ 40%				
Severely disabled, requires hospital care					
Requires hospital care and supportive treatment					
Moribund, disease progressing rapidly					
MSKCC risk (second line line) (the definition of 2 nd line MSKCC is	reachable via a click)				
☐ Good ☐ Poor					
□ Intermediate □ NA					

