ADONIS CRF Subject ID: Tumor second line treatment Therapy started with Axitinib in 2nd line Therapy started with Axitinib on ☐ 5 mg/2x/day Dose: other: Additional anti-tumor treatment (e.g. bisphosphonates, other) □ No ☐ Yes Il yes please complete the table : Medication Dosage Starting date Status ____/ □ Ongoing □ Discontinued (MM/YYYY) (trade name) (unit) End date : _ _ / _ _ _ _ (MM/YYYY) ____/ □ Ongoing □ Discontinued (MM/YYYY) (trade name) (dose) (unit) End date : _ _ / _ _ _ _ (MM/YYYY) (if the patients started the study with Sunitinib, the table completed during SU follow up is displayed to be updated - new lines can be added if more than 2 medications are received) Radiotherapy ☐ Yes □ No If the patient is enrolled in the study when AXITINIB is started, please complete the page "Prior treatment with Sunitinib in first line" If the patient was enrolled in the study when SUNITINIB was started in first line, please complete the page "Follow-up visit with Axitinib" at each visit until discontinuation of Axitinib (approximately every 1 month) Please, remit the quality of life questionnaire to the patient and ask him/ her to complete it at every month at home (i.e Day 0 Day 30 Day 60 etc.)

ADONIS CRF Subject ID: Prior treatment with Sunitinib in first line Please only fill in this section, if patient is enrolled In the study at Axitinib start Baseline characteristics at the start of Sunitinib Eastern Cooperative Oncology Group (ECOG) available ☐ Yes □ No If yes, □1 □ 2 □ 0 □ 3 □ 4 MSKCC risk (first line) (the definition of 1st line MSKCC is reachable via a click on the study website) □ Good □ Poor □ Intermediate \sqcap NA Heng risk factors (the definition is reachable via a click on the study website) □ Good □ Poor □ Intermediate □ NA At Sunitinib initiation, medical history of hypertension? ☐ Yes □ No At Sunitinib initiation was patient receiving an antihypertensive treatment? ☐ Yes □ No Therapy with Sunitinib in first line ___/ __/ ___ (DD/MMYYYY) Therapy started with Sunitinib on Dose at initiation:

50 mg/day, 4 weeks, then paused for 2 weeks other: ___/ __/ ___ (DD/MMYYYY) Therapy discontinuation on Efficacy What was the best response with Sunitinib (according to RECIST criteria (v1.1)? □ CR (Complete Remission) Date Date □ PR (Partial Remission) □ SD (Stable Disease) □ PD (Progressive Disease) □ NA (Not Assessable) Reason:

ADONIS CRF							Subject ID:
Changes in d	osage	and sched	dule				

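### The eCRF has no adverse-event question for sunitinib-enrolled patients when they start axitinib, and the study plan and Section 8.2 contradict the long-term form on safety collection after treatment stops

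*Protocol*

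**What the plan says.** Protocol 10.1 sets the requirement. Its table asks for all serious and all non-serious AEs to be recorded on the eCRF. Reporting starts at the first dose (or at consent, if the patient is already exposed). It then "lasts through the end of the observation period of the study, which must include at least 28 calendar days following the last administration" (either study drug). Separately, the events listed in the table "must be reported to Pfizer within 24 hours of awareness of the event by the investigator".

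The Annex 1 study plan (1.2) marks Safety at the SU and AXI initiation and follow-up visits. It leaves the cell blank under "Long term follow up". The mark at AXI initiation does not carry the footnote symbol that limits some rows to patients enrolled at AXI start.

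The AXI initiation form (CRF 4.1) has two routes. For patients already in the study it says: "If the patient was enrolled in the study when Sunitinib started in first line, please only fill in sections that" need updating. The retrospective section on prior sunitinib opens with: "Please only fill in this section, if patient is enrolled In the study at Axitinib start".

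Section 8.2 says of patients who come off SU without receiving AXI, or who come off AXI, that "they will be followed up every 6 months (separate form) for survival until the end of the study".

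**The concern.** In a non-interventional study without protocol visits, AE capture depends largely on what each form asks. Two stretches of the 10.1 reporting period are poorly served: the interval between stopping SU and starting AXI in patients enrolled at SU start, and the weeks after the last dose of study drug.

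The 24-hour route does not fill the gap. Outside Switzerland, 10.1 and 10.2 confine 24-hour reporting of non-serious AEs to listed risk-management items. An ordinary non-serious AE has the eCRF as its only required route. Protocol 8.7.3 and SAP 8.2.1 plan tables of all AEs, related or not, by treatment period, and an event that no form elicits may never reach them.

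**Working it through.** The documents state no figure to reproduce. The check is a form-by-form comparison for a patient enrolled at SU start.

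| Stage | Study plan, Safety row | AE question on the form |
|---|---|---|
| SU follow-up (CRF 3.2), including the visit at which SU is stopped | Marked | All AEs since the last visit |
| AXI initiation (CRF 4.1) | Marked, without the footnote | None open to this patient |
| AXI follow-up (CRF 4.2) | Marked | Sunitinib-related AEs only |
| Long-term follow-up (CRF 5) | Blank | Yes/No on AEs, with a reminder of the reporting rules |
| Study discontinuation (CRF 6) | No column | None |

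**Window 1: between SU and AXI.**
1. The 10.1 period runs without a break from first dose to the end of observation, so this interval lies inside it.
2. The last all-AE question is at the visit where SU is stopped.
3. The long-term form does not apply. Section 8.2 reserves it, after SU, for patients not receiving AXI, and CRF 3.2 sends AXI starters to the AXI initiation form.
4. On that form, the only AE question is in the section reserved for patients enrolled at AXI start. It covers sunitinib-related events during the SU course.
5. The next form, AXI follow-up, is expected after about 4 weeks. Its question is limited to sunitinib-related AEs, so an event in the gap that is not attributed to SU is never asked about. Read literally, the same question also does not ask about AEs attributed to AXI.

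Number of patients concerned, from Protocol 8.5: 525 enrolled at SU start x 68% receiving a second line = 357; 357 x 35% starting AXI = 125.

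**Window 2: after the last dose.**
1. A blank Safety cell and a survival-only purpose in 8.2 say that no safety data are collected at long-term follow-up. The form asks about AEs. These passages cannot all be followed.
2. Timing: 6 months x 30.44 days = 183 days. If the first long-term form is completed 6 months after the last dose, it comes 183 - 28 = 155 days after the 28-day minimum has ended.

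**The case against.** The strongest reply is that 10.1 does not depend on any form. It requires all AEs on the eCRF whatever the visit, asks the investigator to pursue information on each AE, and requires AEs related to study drug to be followed until they resolve or stabilise. This stands as a duty and limits the damage. It does not replace an AE question, because the duty starts with awareness and a prompt is one of the main ways a site becomes aware.

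It is also fair to say that the window after the last dose is not empty. The long-term form asks about AEs, and a discontinuation visit held after the last dose may cover part of the 28 days.

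A reader might infer several stronger things that the documents do not support:
- **That SU and AXI incidence is biased downward, most of all in patients stopping for intolerability.** The treatment forms record intolerability as the reason for stopping. SAP 8.2.1 counts each term once per patient, so later evolution of a recorded event does not change its incidence. The SAP also does not say to which treatment period off-drug events belong.
- **That capture will differ by site according to which document a site follows.** All physicians use one eCRF, and it contains the long-term AE question.
- **That AEs on the long-term form carry no grade.** That block is visibly broken in the text available, so missing rows prove nothing.
- **That the 28 days can be expressed as a share of time on AXI plus 28 days.** The required period runs to the end of observation, with 28 days only as a minimum, so that denominator is wrong.

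**Conclusion.** The concern holds as a mismatch between the safety requirement and the forms, with a risk of missed AEs. It does not show that AEs have been lost or rates distorted.

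The SU-to-AXI interval is the firmer part. The study plan promises safety collection at AXI initiation that the form does not provide to about 125 planned patients. The number of AEs at risk cannot be estimated, because the documents do not give the length of the interval, and for some patients it may be short.

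The post-treatment part is smaller. The study plan and Section 8.2 contradict the long-term form, and the 6-monthly interval is poorly matched to a 28-day window.

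The conclusion assumes that the Annex 1 forms represent the live eCRF and that no AE question on the AXI initiation form was lost when the text was extracted.

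**What to change.** - **AXI initiation form (CRF 4.1):** for patients enrolled at SU start, add the block already used on the SU follow-up form, asking for AEs since the last visit with description, start date and CTCAE grade.
- **AXI follow-up form (CRF 4.2):** reword the AE question to ask about all AEs since the last visit, whatever the suspected cause.
- **Study plan (1.2) and Section 8.2:** mark Safety in the long-term follow-up column and extend the stated purpose of that follow-up to survival and safety.
- **First long-term form (CRF 5):** ask specifically about the 28 days after the last dose of SU or AXI, completed from routine records.

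The cost is one reused block, one reworded question, one study-plan cell, one phrase in 8.2 and one added prompt. Sites enter slightly more data. No visit or procedure is added, so the study stays non-interventional.

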10.2. COUNTRY REQUIREMENT

10.2.1. Switzerland requirements:

Because of the inclusion criteria (Patients being treated with SU in 1st line and/or being treated with AXI in 2nd line after having received Su in 1st line), the medication is prescribed within the regular practice of the physician. Because of the non-interventional nature of the study, there will be no specific requirements with regards to the treatment process. The physician will determine dosage and duration of the treatment, guided by the Swiss Prescribing Information and according to his assessment of the individual therapeutic needs of the patient.

Safety event	Recorded on the eCRF of the Study	Reported on the NIS AEM Report Form to Pfizer Safety within 24 hours of awareness					
SAE	A11	All					
non-serious AE	All	All					
Scenarios involving exposure to a drug under study, including exposure during pregnancy, exposure during breast feeding, medication error, overdose, misuse, extravasation; lack of efficacy; and occupational exposure	All (regardless of whether associated with an AE), except occupational exposure	All (regardless of whether associated with an AE)					

10.2.2. Spain requirements:

The following table summarizes the requirements for recording adverse events / adverse reactions on the eCRF of the study and reporting adverse events / adverse reactions on the non-interventional adverse event form (NIS AEM Report Form) to the department of safety of the Pfizer drug. These requirements are described for three types of events: (1) severe adverse events (SAE); (2) non-severe AE (as applicable); and (3) cases involving exposure to the drug, including exposure during pregnancy, exposure during lactation, medication error, overdose, misuse, extravasation, and occupational exposure. These events are defined in the "Definitions of adverse events" section.

Safety event	Recorded on the eCRF of the Study	Reported on the NIS AEM Report Form to Pfizer Safety within 24 hours of awareness
SAE	A11	A11

1	I	Potential risks (SUNITINIB RMP V14.0)					
		Carcinogenicity					
		Other Potential Cardiac events: Conduction defect events, Ischemic events, Tachycardia events					
1		Retinal detachment					
		Reproductive and developmental toxicity					
		Missing Information (SUNITINIB RMP V14.0)					
		Use in pediatric subjects					
		Use in pregnant and lactating women					
		Use in severe hepatic impairment subjects					
		Use in cardiac impairment subjects					
		Potential risks (AXITINIB RMP V8.0)					
		Wound healing complications					
		Congestive heart failure/cardiomyopathy					
		QT prolongation					
		Reproductive and developmental toxicity					
non-serious AE	A11	Microangiopathy					
		Carcinogenicity					
		Osteonecrosis of the jaw					
		Drug Drug interactions with CYP1A2, CYP2C8 and P-glycoprotein substrates Missing information (AXITINIB RMP V8.0)					
		Risks in pregnant and lactating women,					
		Risks in pediatric subjects,					
		Risks in patients with moderate and severe renal impairment (serum creatinine >1.5 times the ULN or calculated creatinine clearance <60 mL/min), Risks in subjects with severe hepatic impairment (>Child-Pugh Class B), Risks in patients with brain metastasis, spinal cord compression, or carcinomatous meningitis,					
		Risks in subjects with recent myocardial infarction, severe/unstable angina, coronary/peripheral artery bypass graft, symptomatic congestive heart failure, cerebrovascular accident or transient ischemic attack, deep vein thrombosis, or pulmonary embolism, Risks in patients with active peptic ulcer disease,					
		Risks in subjects with a recent major surgery (within 4 weeks) or radiation therapy (within 2 weeks).					

Scenarios involving exposure to a drug under study, including exposure during pregnancy, exposure during breast feeding, medication error, overdose, misuse, extravasation; lack of efficacy; and occupational exposure	All (regardless of whether associated with an AE), except occupational exposure	All (regardless of whether associated with an AE)
---	--	---

In addition to the notification to the Pfizer safety department, suspected serious adverse reactions detected during the course of the study will be notified to the point of contact designated by the competent bodies in term of pharmacovigilance of the autonomous community from where the health professional exercises, within a maximum period of 15 calendar days since the suspicion of adverse reaction was known. This notification will be made electronically by the Pfizer pharmacovigilance manager.

Adverse Reactions (AR)

An AR is any harmful and unintended reaction to a research drug, regardless of the dose administered. Unlike an AA, in the case of an adverse reaction, there is a suspicion of a causal relationship between the investigational drug and the adverse event, and there is also talk of suspected RA (SAR).

10.3. DEFINITIONS OF SAFETY EVENTS

Adverse events

An AE is any untoward medical occurrence in a patient administered a medicinal product. The event need not necessarily have a causal relationship with the product treatment or usage. Examples of adverse events include but are not limited to:

 Abnormal test findings (see below for circumstances in which an abnormal test finding constitutes an adverse event/AR*);

^{*} Spain requirement only

- · Clinically significant symptoms and signs;
- Changes in physical examination findings;
- Hypersensitivity;
- Lack of efficacy;
- Drug abuse;
- Drug dependency.

Additionally, for medicinal products, they may include the signs or symptoms resulting from:

- Drug overdose;
- · Drug withdrawal;
- Drug misuse;
- Off-label use;
- Drug interactions;
- Extravasation;
- Exposure during pregnancy;
- Exposure during breast feeding;
- Medication error;
- Occupational exposure.

Abnormal test findings

The criteria for determining whether an abnormal objective test finding should be reported as an adverse event/AR* are as follows:

- Test result is associated with accompanying symptoms, and/or
- · Test result requires additional diagnostic testing or medical/surgical intervention, and/or

Pfizer Confidential Page 41 of 108

Spain requirement only

- Test result leads to a change in study dosing or discontinuation from the study, significant additional concomitant drug treatment, or other therapy, and/or
- Test result is considered to be an adverse event by the investigator or sponsor.

Merely repeating an abnormal test, in the absence of any of the above conditions, does not constitute an adverse event/AR*. Any abnormal test result that is determined to be an error does not require reporting as an adverse event/AR*.

Serious adverse events/SAR*

A serious adverse event/SAR* is any untoward medical occurrence in a patient administered a medicinal or nutritional product (including pediatric formulas) at any dose that:

- Results in death;
- Is life-threatening;
- Requires inpatient hospitalization or prolongation of hospitalization (see below for circumstances that do not constitute adverse events/AR*);
- Results in persistent or significant disability/incapacity (substantial disruption of the ability to conduct normal life functions);
- Results in congenital anomaly/birth defect.

Progression of the malignancy under study (including signs and symptoms of progression) should not be reported as a serious adverse event/SAR* unless the outcome is fatal within the safety reporting period. Hospitalization due to signs and symptoms of disease progression should not be reported as a serious adverse event/SAR*. If the malignancy has a fatal outcome during the study or within the safety reporting period, then the event leading to death must be recorded as an adverse event/SAR* and as a serious adverse/SAR* event with severity Grade 5.

Medical and scientific judgment is exercised in determining whether an event/reaction* is an important medical event. An important medical event may not be immediately life-threatening and/or result in death or hospitalization. However, if it is determined that the event/reaction* may jeopardize the patient or may require intervention to prevent one of the other outcomes listed in the definition above, the important medical event should be reported as serious.

^{*} Spain requirement only

Axitinib, Inlyta[®]
A4061078 NON-INTERVENTIONAL STUDY PROTOCOL
ADONIS Amended V13
28 Sept 2017

Examples of such events are intensive treatment in an emergency room or at home for allergic bronchospasm; blood dyscrasias or convulsions that do not result in hospitalization; or development of drug dependency or drug abuse.

Additionally, any suspected transmission via a Pfizer product of an infectious agent, pathogenic or non-pathogenic, is considered serious. The event/reaction* may be suspected from clinical symptoms or laboratory findings indicating an infection in a patient exposed to a Pfizer product. The terms "suspected transmission" and "transmission" are considered synonymous. These cases are considered unexpected and handled as serious expedited cases by PV personnel. Such cases are also considered for reporting as product defects, if appropriate.

Hospitalization

Hospitalization is defined as any initial admission (even if less than 24 hours) to a hospital or equivalent healthcare facility or any prolongation to an existing admission. Admission also includes transfer within the hospital to an acute/intensive care unit (e.g., from the psychiatric wing to a medical floor, medical floor to a coronary care unit, neurological floor to a tuberculosis unit). An emergency room visit does not necessarily constitute a hospitalization; however, an event leading to an emergency room visit should be assessed for medical importance.

Hospitalization in the absence of a medical AE/AR* is not in itself an AE/AR* and is not reportable. For example, the following reports of hospitalization without a medical AE are not to be reported.

- Social admission (e.g., patient has no place to sleep)
- Administrative admission (e.g., for yearly exam)
- Optional admission not associated with a precipitating medical AE (e.g., for elective cosmetic surgery)
- Hospitalization for observation without a medical AE
- Admission for treatment of a pre-existing condition not associated with the development of a new AE or with a worsening of the pre-existing condition (e.g., for work-up of persistent pretreatment lab abnormality)

_

^{*} Spain requirement only

 Protocol-specified admission during clinical study (e.g., for a procedure required by the study protocol)

Scenarios necessitating reporting to Pfizer Safety within 24 hours

Scenarios involving exposure during pregnancy, exposure during breastfeeding, medication error, overdose, misuse, extravasation, lack of efficacy, and occupational exposure are described below

Exposure during pregnancy

An exposure during pregnancy (EDP) occurs if:

 A female becomes, or is found to be, pregnant either while receiving or having been exposed to (e.g., environmental) Sunitinib and/or Axitinib, or the female becomes, or is found to be, pregnant after discontinuing and/or being exposed to Sunitinib and/or Axitinib (maternal exposure).

An example of environmental exposure would be a case involving direct contact with a Pfizer product in a pregnant woman (e.g., a nurse reports that she is pregnant and has been exposed to chemotherapeutic products).

A male has been exposed, either due to treatment or environmental exposure to Sunitinib
and/or Axitinib prior to or around the time of conception and/or is exposed during the
partner pregnancy (paternal exposure).

As a general rule, prospective and retrospective exposure during pregnancy reports from any source are reportable irrespective of the presence of an associated AE and the procedures for SAE/SAR* reporting should be followed.

If a study participant or study participant's partner becomes, or is found to be, pregnant during the study participant's treatment with *Sunitinib and/or Axitinib*, this information must be submitted to Pfizer, irrespective of whether an adverse event has occurred using the NIS AEM Report Form and the EDP Supplemental Form.

In addition, the information regarding environmental exposure to *Sunitinib and/or Axitinib* in a pregnant woman (e.g., a subject reports that she is pregnant and has been exposed to a cytotoxic product by inhalation or spillage) must be submitted using the NIS AEM Report Form and the EDP supplemental form. This must be done irrespective of whether an AE has occurred.

_

^{*} Spain requirement only

Information submitted should include the anticipated date of delivery (see below for information related to termination of pregnancy).

Follow-up is conducted to obtain general information on the pregnancy; in addition, follow-up is conducted to obtain information on EDP outcome for all EDP reports with pregnancy outcome unknown. A pregnancy is followed until completion or until pregnancy termination (e.g., induced abortion) and Pfizer is notified of the outcome. This information is provided as a follow up to the initial EDP report. In the case of a live birth, the structural integrity of the neonate can be assessed at the time of birth. In the event of a termination, the reason(s) for termination should be specified and, if clinically possible, the structural integrity of the terminated fetus should be assessed by gross visual inspection (unless pre-procedure test findings are conclusive for a congenital anomaly and the findings are reported).

If the outcome of the pregnancy meets the criteria for an SAE (e.g., ectopic pregnancy, spontaneous abortion, intrauterine fetal demise, neonatal death, or congenital anomaly [in a live born, a terminated fetus, an intrauterine fetal demise, or a neonatal death]), the procedures for reporting SAEs should be followed.

Additional information about pregnancy outcomes that are reported as SAEs/SAR* follows:

- Spontaneous abortion includes miscarriage and missed abortion;
- Neonatal deaths that occur within 1 month of birth should be reported, without regard to
 causality, as SAEs. In addition, infant deaths after 1 month should be reported as
 SAEs/SAR* when the investigator assesses the infant death as related or possibly related
 to exposure to investigational product

Additional information regarding the exposure during pregnancy may be requested. Further follow-up of birth outcomes will be handled on a case-by-case basis (e.g., follow-up on preterm infants to identify developmental delays).

In the case of paternal exposure, the study participant will be provided with the Pregnant Partner Release of Information Form to deliver to his partner. It must be documented that the study participant was given this letter to provide to his partner.

_		4 40 40
LVDACHTA	dinera co	broacttooding
LADOSILE	чшше	breastfeeding

Spain requirement only

Scenarios of exposure during breastfeeding must be reported, irrespective of the presence of an associated AE/RA*. An exposure during breastfeeding report is not created when a Pfizer drug specifically approved for use in breastfeeding women (e.g., vitamins) is administered in accord with authorized use. However, if the infant experiences an AE/RA* associated with such a drug's administration, the AE/RA* is reported together with the exposure during breastfeeding.

Medication error

A medication error is any unintentional error in the prescribing, dispensing or administration of a medicinal product that may cause or lead to inappropriate medication use or patient harm while in the control of the health care professional, patient, or consumer. Such events may be related to professional practice, health care products, procedures, and systems including: prescribing; order communication; product labeling, packaging, and nomenclature; compounding; dispensing; distribution; administration; education; monitoring; and use.

Medication errors include:

- Near misses, involving or not involving a patient directly (e.g., inadvertent/erroneous administration, which is the accidental use of a product outside of labeling or prescription on the part of the healthcare provider or the patient/consumer);
- Confusion with regard to invented name (e.g., trade name, brand name).

The investigator must submit the following medication errors to Pfizer, irrespective of the presence of an associated AE/SAE:

- Medication errors involving patient exposure to the product, whether or not the medication error is accompanied by an AE.
- Medication errors that do not involve a patient directly (e.g., potential medication errors or near misses). When a medication error does not involve patient exposure to the product the following minimum criteria constitute a medication error report:
 - An identifiable reporter;
 - A suspect product;
 - The event medication error.

Overdose, Misuse, Extravasation

Reports of overdose, misuse, and extravasation associated with the use of a Pfizer product are reported to Pfizer by the investigator, irrespective of the presence of an associated AE/SAE.

Lack of Efficacy

Reports of lack of efficacy to a Pfizer product are reported to Pfizer by the investigator, irrespective of the presence of an associated AE/SAE or the indication for use of the Pfizer product.

Occupational Exposure

Reports of occupational exposure to a Pfizer product are reported to Pfizer by the investigator, irrespective of the presence of an associated AE/SAE.

